5.6. Derived and Transformed Data

5.6.1. Calculations Using Dates

5.6.1.1. Baseline Age

Age for enrolled subjects will be calculated as the truncated difference (eg, fractional part ignored) between the date of the ICF and the subject's birth date adjusted for years (ie, AGE = int[(ICF date of this study- date of birth + 1 day) / 365.25]).

5.6.1.2. Study Day

Study Day 1 denotes the day of the first dose of study drug in Study AT1001-036 and is the reference start date for all analyses in this study. Study days (or visit days) are defined relative to Day 1 unless otherwise specified. Days prior to Day 1 are negative and days after Day 1 are positive. There is no Day 0. That is,

Relative Day = (Date of Assessment) – (Date of First Dose of Study Drug) + 1, if assessment is on or after the date of first dose of study drug;

Relative Day = (Date of Assessment) – (Date of First Dose of Study Drug), if assessment is before the date of first dose of study drug.

5.6.1.3. Other Calculations Using Dates

Total duration of treatment will be calculated as the difference between the dates of last and first dose of study drug plus 1 day, regardless of any study drug interruption.

All other calculations of duration for enrolled subjects (eg, time since the primary diagnosis or age of first diagnosis) will be performed relative to the first dose of study drug and will follow the algorithm:

Duration = (Target Date – First Dose Date + 1).

5.6.1.4. Change from Baseline

For any parameter at a specific visit, change from baseline is calculated as the value of the parameter at the specific visit minus the baseline value of that parameter, as defined above.

5.6.1.5. Visit Windows

There will be no derivation for visit windows in terms of summary assessments. Nominal visits will be used for by-visit tables. For data with repeated observations at a given visit (eg, laboratory assessments), the earliest of the available non-missing values at a visit should be used in summary tables. Other observations will be considered as unscheduled visits.

5.6.1.6. Multiple Assessments

If multiple assessments are associated with a nominal visit post-baseline, the first assessment will be used.

5.7. Handling of Missing Data

5.7.1. Missing Start and Stop Dates for Adverse Events

For AEs, partially missing start dates will be imputed for the purpose of determining treatment emergence only.

Partially missing start dates will be imputed as follows:

For a missing day,

- If the month and year are equal to the month and year of the date of the first dose of study drug, then the date of the first dose of study drug will be used.
- Otherwise, the first day of the month will be used.

For a missing day and month or just missing month,

- If the year is equal to the year of the first dose of study drug, then the date of the first dose of study drug will be used.
- Otherwise, the first day of the month and the first month of the year will be used.

If the stop date is not missing and the imputed start date is after the stop date, then the stop date will be used.

If the start date is completely missing and the stop date is on or after the date of first dose of study drug, the AE will be considered a TEAE.

If both the start date and stop date are missing, the AE will be considered a TEAE.

Missing stop dates for AEs will not be imputed.

These imputations will be applied only to the AE summary tables. Listings will show the data as collected.

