10.1. Definitions

10.1.1. Adverse Event

An AE is defined as any untoward medical occurrence in a subject or clinical investigation subject administered a pharmaceutical product and which does not necessarily have a causal relationship with this treatment. An AE can therefore be any unfavorable and unintended sign, symptom, or disease temporally associated with the use of a medicinal product, whether or not considered related to the medicinal product.

Therefore, AEs include the following:

- The onset of new signs, symptoms, conditions, and illnesses
- Exacerbation of pre-existing conditions or illnesses
- Abnormal laboratory findings deemed clinically significant by the investigator
- Physical examination changes deemed clinically significant by the investigator
- Abnormal medical evaluation findings (eg, ECG) that are not documented at baseline and/or, in the investigator's opinion, represent a clinically significant change in the subject's health during study participation
 - Baseline medical evaluation findings (eg, ECG) that were not previously provided as medical history and can be determined as starting before baseline, are not considered AEs and will be recorded as medical history.

Adverse events will be recorded in the eCRF and subject's source record beginning from the time written consent (assent) is provided through the follow-up visit (at least 30 days after the last dose of study drug).

Subjects will be enrolling in this study following completion of Study AT1001-020. Therefore:

- Adverse events that are ongoing as of the last study visit of Study AT1001-020 will be entered in the AE eCRF.
 - The start date recorded in Study AT1001-020 will be the start date entered in the current study AE eCRF.
 - The event will be noted as continuing from Study AT1001-020 in the current study's AE eCRF.

A single diagnosis should be entered when known. If a clear diagnosis cannot be determined at the time of eCRF completion and the subject's source record entry, each sign and symptom must be recorded individually, until a final diagnosis is established. Conditions, signs, symptoms, etc that are present in the subjects' medical history at baseline should only be reported as AEs if they worsen (ie, increase in severity) since baseline.
Adverse events that begin after the first dose of investigational product in Study AT1001-036 will be considered treatment-emergent adverse events (TEAEs).

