9.2. Adverse Events

A TEAE is defined as any untoward medical occurrence in a subject or clinical investigation subject administered a pharmaceutical product and which does not necessarily have a causal relationship with this treatment and that begins on or after the date of the first dose of study drug in the 036 study.

Treatment-related TEAEs are defined as TEAEs that have an Investigator-defined relationship to treatment of "Definite", "Probable" or "Possible". Events with an investigator-defined relationship of "Unrelated" or "Unlikely Related" are considered as not related to treatment.

Serious TEAEs are defined as TEAEs that have a "yes" response to the eCRF question "Event Serious?". Serious adverse events are categorized as "Death", "Life-threatening", "Requires/Prolongs Hospitalization", "Disability/ Incapacity", "Congenital Anomaly/Birth Defect" or "Important Medical Event or Reaction".

An overall summary of TEAEs, will be tabulated, including the number and percentage of subjects reporting, by sex and overall:

- TEAEs
- Treatment-related TEAEs
- SAEs
- TEAEs leading to discontinuation of study drug
- TEAEs leading to death

The number of events and incidence rates will also be provided in the overall summary table. Incidence rate is calculated as: total events divided by the total patient years of exposure. Total patient years of exposure are the sum of the duration of exposure in years for all subjects.

Further, the following TEAE summaries will be provided by sex and overall:

- Any TEAEs by SOC and PT
- Any TEAEs by PT
- Treatment-related TEAEs by SOC and PT
- TEAEs by severity, by SOC and PT
- Serious TEAEs by SOC and PT
- Any non-serious TEAE by PT

When presenting summaries by SOC and PT, subjects are counted only once within each SOC and PT. TEAEs will be presented alphabetically by SOC and PT.

When presenting summaries by PT, subjects are counted only once in each PT. TEAEs will be presented in the order of descending frequency in the overall group.

When presenting summaries by severity, if a subject has more than one event within a given SOC or PT at different severities, the maximum severity will be tabulated. For example, if a subject had two events with the same PT, but one was moderate and the other severe, the severe TEAE will be included in the tabulation.

Subject listings will be provided for all AEs, TEAEs leading to discontinuation of study drug, TEAEs with an outcome of death, and SAEs.

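### SAP 5.7.1 ignores the record that an adverse event continues from AT1001-020, so carry-over events with a partial or missing start date can be counted as treatment-emergent in this study

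*SAP*

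**What the plan says.** Protocol 10.1.1 deals with the roll-over from the parent study in three steps. First, "Adverse events that are ongoing as of the last study visit of Study AT1001-020 will be entered in the AE eCRF". Second, "The start date recorded in Study AT1001-020 will be the start date entered in the current study AE eCRF", so a partial date in the parent study stays partial here. Third, "The event will be noted as continuing from Study AT1001-020". The same section defines a TEAE as an event beginning after the first AT1001-036 dose.

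SAP 9.2 counts an event as treatment-emergent if it "begins on or after the date of the first dose of study drug in the 036 study". It makes no exception for continuing events.

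SAP 5.7.1 imputes partial start dates solely to decide treatment emergence:

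- **Day missing:** if month and year match those of first dose, onset becomes the first-dose date. Otherwise it is the first of the month.
- **Month missing, with or without the day:** "If the year is equal to the year of the first dose of study drug, then the date of the first dose" is used. Otherwise onset is 1 January of the recorded year.
- **Start wholly missing:** the event is a TEAE if it stopped on or after first dose. In addition, "If both the start date and stop date are missing, the AE will be considered a TEAE".
- **Stop-date guard:** if the imputed start falls after a known stop date, the stop date is used instead.

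The imputations apply to the summary tables, while listings keep the dates as collected. Neither SAP 5.7.1 nor SAP 9.2 refers to the continuation record, and nothing else in the SAP uses it.

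**The concern.** Moving an unknown onset to the first-dose date is a sensible precaution when nothing else shows whether the event came before or after treatment. Here something else does. An event ongoing at the last AT1001-020 visit began before the first AT1001-036 dose, and the protocol has the site record that fact. The imputation rule can override it.

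Safety is the primary objective, and TEAE incidence is the first safety endpoint listed. A misclassified event can appear in the overall, related, serious, severity, system organ class and preferred term tables of SAP 9.2. It also enters the incidence-rate numerator, while the denominator is exposure in this study. Enrollment is meant to follow AT1001-020 without a gap (Protocol 7.1), so late parent-study onsets will often share the calendar month or year of first dose.

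**Working it through.** The documents give no figure to reproduce. The check applies SAP 5.7.1 and the SAP 9.2 test (onset on or after the first-dose date) literally to events whose true onset precedes first dose.

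**Step 1. Is onset known?** The event was ongoing at the last AT1001-020 visit (Protocol 10.1.1). That visit supplies the baseline, which is taken before dosing on Day 1 (Protocol 9.1.2). Onset therefore precedes first dose.

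**Step 2. Examples, with an illustrative first dose on 15 Sep 2020.**

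| Recorded start | Stop | Onset used | Class |
|---|---|---|---|
| 03 Sep 2020 | none | 03 Sep 2020 | not TEAE |
| Sep 2020, no day | none | 15 Sep 2020 | **TEAE** |
| Aug 2020, no day | none | 01 Aug 2020 | not TEAE |
| 2020 only | none | 15 Sep 2020 | **TEAE** |
| 2020 only | 01 Oct 2020 | 15 Sep 2020 | **TEAE** |
| 2020 only | 14 Sep 2020 | 14 Sep 2020 | not TEAE |
| 2019 only | none | 01 Jan 2019 | not TEAE |
| wholly missing | none, or 01 Oct 2020 | not imputed | **TEAE** |

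**Step 3. Share converted, given the kind of missing date.** Assumptions, none of them from the documents: the event is still ongoing at first dose, onset is uniform over the W days before first dose, and first doses are spread evenly over a 365-day year. Let d be the day of the month and j the day of the year of first dose.

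- *Day missing:* the share for one first-dose date is min(d − 1, W)/W. Over the year, d − 1 sums to 7 × 465 + 4 × 435 + 378 = 5,373, a mean of 5,373/365 = 14.72 days. For W of 30 or more the average share is 14.72/W.
- *Month missing:* the share is min(j − 1, W)/W. Its average is [W(W + 1)/2 + (364 − W)W]/(365W) = (364.5 − W/2)/365.

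| Date pattern | W = 30 | W = 90 | W = 180 | W = 365 |
|---|---|---|---|---|
| Complete | 0% | 0% | 0% | 0% |
| Day missing | 49.1% | 16.4% | 8.2% | 4.0% |
| Month missing | 95.8% | 87.5% | 75.2% | 49.9% |
| Start wholly missing | 100% | 100% | 100% | 100% |

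For example, with the month missing and W = 30, (364.5 − 15)/365 = 95.8%. This pattern depends heavily on the calendar. At W = 365, a first dose on 31 December gives 364/365 = 99.7%, and one on 2 January gives 1/365 = 0.3%.

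**Step 4. Effect on the tables.** One converted event adds at most 1/N to its preferred term. N is not in the documents. For an assumed N of 10 to 30, that is at most 1/10 = 10 to 1/30 = 3.3 percentage points. It is a ceiling because SAP 9.2 counts a subject once per preferred term: a subject who already has a TEAE under that term adds nothing. In the event count and the incidence-rate numerator, each converted event adds one.

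**Step 5. With the fix.** If events recorded as continuing are classed before any imputation, 0% are converted under every pattern.

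**The case against.** The strongest reply is that few events may be exposed. The AT1001-020 start date has to be carried forward, Protocol 13.1 asks for an explanation of missing data, and Protocol 13.2 requires data cleaning. That stands. The documents give no count of carry-over events or of partial dates, so the change in TEAE incidence cannot be computed.

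A second reply is that the error is cautious: it overstates TEAEs, in keeping with SAP 5.7.2, which assumes the worst for missing severity, relationship and seriousness. The direction is as described. But that logic fits unknown facts, and here the timing is known. Listings show dates as collected, so a careful reader could find the affected cases. This limits the harm, though tables and listings would then disagree. The study is descriptive, without p-values, and the documents list the safety endpoints without ranking them.

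The stop-date guard helps only when the event stopped before first dose.

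A reader might infer that every event carried over from AT1001-020 becomes a TEAE. Step 2 shows otherwise. A reader might also take the percentages as inflation of the TEAE rate. They are shares of carry-over events that already have a given kind of missing date, under an assumed onset window.

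The window itself is uncertain. Protocol 9.2.1 treats events with onset at least 90 days before Visit 1 as medical history, and how this fits with Protocol 10.1.1 is unclear. If such events stay off the AE form, fewer events are exposed, but the windows of 90 days or less apply and the shares are the higher ones.

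A bare exclusion would carry its own risk. Protocol 10.1.1 counts exacerbation of an existing condition as an AE. If a site updates the continuing entry instead of opening a new one, a true post-dose worsening would drop out of the TEAE tables.

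**Conclusion.** The point holds in a limited form. For carry-over events whose start date is partial within the month or year of first dose, or wholly missing, SAP 5.7.1 yields a classification that contradicts the record Protocol 10.1.1 requires. Unless a stop date before first dose is recorded, such events are wrongly counted as TEAEs in the summary tables and in the incidence-rate numerator.

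The mechanism follows from the text alone. Its size does not: the conversion shares rest on the uniform-onset assumption, the percentage-point ceiling rests on an assumed N, and the number of affected events is unknown. The documents do not support a claim that the safety conclusions would change. The correction is still worth making before database lock, because this is a roll-over study in which the protocol foresees exactly this case.

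**What to change.** Open SAP 5.7.1 with:

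> *AEs recorded on the eCRF as continuing from Study AT1001-020 are not treatment-emergent, whatever part of the start date is missing, and their start dates are not imputed; the rules below apply to all other AEs. A worsening of a continuing AE after the first AT1001-036 dose is recorded as a new AE with its own onset date and is assessed as a TEAE.*

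Repeat the worsening instruction in the eCRF Completion Guidelines mentioned in Protocol 10.4.1, since sites do not work from the SAP. Align the TEAE definitions as well: the protocol says after the first dose, while SAP 9.2 includes the whole first-dose date.

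The cost is two SAP sentences and, if the continuation note is a coded eCRF field, one programming condition. The documents do not show the form. If the note is free text, the events would have to be identified by review or by matching to the AT1001-020 AE data. No new data are needed for the exclusion. Entries already made for continuing events should be checked for worsening recorded by updating the old entry.

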5.7.2. Missing Adverse Event Severity, Relationship, and Seriousness

If an AE is missing the severity or relationship to study drug, the AE will be classified under the maximum severity (ie, severe) or the maximum relationship (ie, definite), respectively. If the serious status is missing for an AE, the event will be assumed to be serious.

5.7.3. Missing Start and Stop Dates for Prior and Concomitant Medications

Partially missing medication start dates will be imputed in a similar manner as described in Section 5.7.1 for imputing missing AE start dates. Missing stop dates for medications will not be imputed. If when using these rules, the imputed start date is after the stop date, then the start date will be left as missing and the medication will be considered a concomitant medication for the purpose of the analysis.

5.7.4. Missing Exposure Dates

A subject's first dose date will be obtained from the first (earliest) dosing diary log record that contains a non-missing date of study drug dosing.

- If the month and day is missing, and the year is the same as the ICF date, the month and days will be imputed as the same date of ICF. Otherwise, January will be imputed for missing months and the 1st of the month will be imputed for missing days.
- If the days are missing and the month and year is the same as the ICF date, the days will be imputed as the same date of ICF. Otherwise, the first of the month will be used.
- If the end date of the last dose is missing, the last dose date will be imputed by adding 2 multiplied by the number of doses dispensed from the last non-missing dispensation date.

5.7.5. Missing Baseline and Demographic Data

If partial dates are present for demographic or baseline data, the following general method will be used to handle them.

- For any missing days or months, the first day of the month or the first month of the year will be used. If the imputed dates are prior to the ICF date, they will be set as the same date of ICF.
- If a year is missing and no other information is available, the date should be set to missing. (Note that missing year of the date of birth is not allowed in the study.)
- For date of diagnosis of Fabry disease, no imputation will be done.

6. Demographic, Other Baseline Characteristics and Medication

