This SAP is created based on Protocol AT1001-036, Amendment 2, 19Aug2021. The purpose of this SAP is to outline the planned analyses by Syneos Health to support the completion of the Clinical Study Report (CSR). This SAP describes in detail the statistical methodology and the statistical analyses to be conducted for the above-mentioned protocol. The planned analyses identified in this SAP are following the International Council for Harmonisation of Technical Requirements for Pharmaceuticals for Human Use (ICH) guidelines E9 (R1) Statistical Principles for Clinical Trials. They will be included in regulatory submissions and/or future manuscripts.

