3.1. Summary of Study Design

This is a long-term, open-label, uncontrolled, multicenter study to evaluate the safety, PD, and efficacy of migalastat treatment in subjects over 12 years of age with Fabry disease and with amenable GLA variants. Subjects will enroll in this study following completion of migalastat Study AT1001-020.

Enrollment in this study should immediately follow completion of Study AT1001-020 in order to maintain the continuity of treatment. As appropriate, assessments performed at the End of Treatment visit for Study AT1001-020 will be utilized for Visit 1 (baseline) assessments for this study.

In order to monitor safety, subsequent visits for this study were initially scheduled every 3 months with monthly interim telephone contacts. Following Amendment 2, the visit schedule was changed to every 6 months, with phone contacts at intervening 3-month intervals.

Subjects will remain on the same dose of migalastat that they were receiving in Study AT1001-020. If a subject's weight decreases to below 43 kg, an unscheduled visit will be arranged 2 to 4 weeks later in order to monitor the subject's weight.

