6.2. Demographic and Other Baseline Characteristics

Demographic and baseline data will be summarized by means of descriptive statistics: continuous variables as mean, SD, median, minimum, and maximum, and categorical variables as frequencies and percentages, based on the enrolled population. Demographic data will include age, sex, race, ethnicity, reproductive potential, height, body weight, and body mass index (BMI). Baseline characteristics will include number of years since diagnosis of Fabry disease, previous use of enzyme replacement therapy (ERT), and previous and current use of angiotensin-converting enzyme inhibitors, renin inhibitors, and angiotensin receptor blockers. The following calculations will be utilized:

- Age = (ICF date date of birth + 1) / 365.25 and truncated to complete years. Age at entry into this study will be re-calculated based on the date of birth recorded in Study AT1001-020
- Weight (in kg) = weight (in pounds) *0.4536
- Height (in cm) = height (in inches) * 2.54
- BMI (kg/m2) = weight(kg)/[(height(cm)/100)²], where m=meters.
- Number of years since diagnosis of Fabry disease = (ICF date of this study date of diagnosis of Fabry disease + 1) / 365.25 and rounded to 1 decimal.
- For any missing days or months, years will be used for the calculation: Number of years since diagnosis of Fabry disease = (year of ICF date of this study – year of date of diagnosis of Fabry disease)
- For missing years, number of years will be missing.
- A month will be defined as 30 days
- ERT status is defined as ERT naïve at baseline and ERT experienced; ERT status is determined based on the subject's ERT status in Study AT1001-020.

All demographic and baseline characteristic data will also be listed.

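### Three SAP missing-date rules give wrong results when triggered: age 0 from a partial birth date, an uncapped last-dose date, and some drugs stopped before first dose classed as concomitant

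*SAP*

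**What the plan says.** **(a) Birth date.** SAP section 5.7.5 fills a missing day or month with the first of the month or January, then adds: "If the imputed dates are prior to the ICF date, they will be set as the same date of ICF". The same section shows that birth dates are covered ("Note that missing year of the date of birth is not allowed in the study") and exempts one date only: "For date of diagnosis of Fabry disease, no imputation will be done". Section 5.6.1.1 computes "AGE = int[(ICF date of this study- date of birth + 1 day) / 365.25", bracket then closed. Section 6.2 adds: "Age at entry into this study will be re-calculated based on the date of birth recorded in Study AT1001-020".

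**(b) Last dose.** SAP section 5.7.4 says that, if the end date is missing, "the last dose date will be imputed by adding 2 multiplied by the number of doses dispensed from the last non-missing dispensation date". It sets no limit at discontinuation, early termination (ET) visit, death or last contact, and makes no deduction for returned capsules. Section 9.1 uses the date for exposure and compliance, and section 9.2 uses exposure as the denominator of the TEAE incidence rate.

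**(c) Medications.** SAP section 5.7.3 imputes partial start dates in the manner of section 5.7.1. If the imputed start then falls after the stop date, the drug counts as concomitant. Section 6.4 reserves that class for drugs continued past first dose or started on or after it. For the same clash in an adverse event, section 5.7.1 takes the stop date as the start. Protocol section 11.4.4.8 has drugs stopped within 2 weeks of the AT1001-020 End of Study Visit recorded as concomitant.

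**The concern.** The SAP is the programming specification, so a rule that returns a wrong value when followed literally should be corrected before it is coded. Here one rule returns an age that no eligible subject can have, one lengthens exposure and never shortens it for an early stopper, and one classifies drugs against the SAP's own definition. At stake are the age row of the demographic table, the exposure and patient-year figures in a study whose primary objective is safety, and the concomitant medication table. A drug started between the true and the imputed last dose would also be counted as concomitant instead of being flagged as a post medication under SAP section 6.4.

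**Working it through.** The plan states no figure of its own here, so the check applies each rule as written.

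**(a) Birth date**
- Every birth date precedes consent, so every partial birth date is moved to the ICF date.
- Age = int[(ICF − ICF + 1)/365.25] = int(0.0027) = 0. Protocol section 8.2.1 requires more than 12 years.
- Illustration: birth year 2005 known, consent 15 Mar 2020. Without the reset, 1 Jan 2005 is used: int(5553/365.25) = 15. Over the 365 possible birth dates in 2005, the SAP formula gives 15 for 75 and 14 for 290, so the repaired rule can still be up to one year high.
- Effect of one case on mean age, assuming a true mean of 15 and a true age of 15 for that subject: 15 × 9/10 = 13.5 with 10 subjects, and 15 × 29/30 = 14.5 with 30. The minimum becomes 0.

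**(b) Last dose**
- Assumptions: resupply at each clinic visit, no overage, first dose of a supply on the dispensing day, doses on schedule. Six-monthly visits of 30-day months give S = 180/2 = 90 doses. Before Amendment 2, "subsequent visits for this study were initially scheduled every 3 months with monthly interim telephone contacts", which gives S = 90/2 = 45.
- True last dose after n doses: 2(n − 1) days after dispensing. Imputed: 2S days. Overshoot = 2S + 2 − 2n days.

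| Supply S | Doses taken n | Overshoot (days) |
|---|---|---|
| 90 | 15 | 152 |
| 90 | 45 | 92 |
| 90 | 90 | 2 |
| 45 | 15 | 62 |
| 45 | 22 | 48 |
| 45 | 45 | 2 |

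- Incidence rate: fall = 1 − PY/(PY + overshoot in years). Assume 10 to 30 subjects with 1.5 years each, so 15 to 45 patient-years, and one triggered case. For 92 days (92/365.25 = 0.252 years): 1.65% at 15 and 0.56% at 45. For 48 days (0.131 years): 0.87% and 0.29%.
- Compliance by SAP section 9.1 reduces to 2 × doses/(duration + 1). For a first 90-dose supply, imputed duration is 181 days. If the numerator is doses taken, n = 45 gives 90/182 = 49.5%. If it is doses dispensed, the result is 180/182 = 98.9%. After six fully taken 45-dose supplies and then 45 of 90, it is (270 + 45)/361 = 87.3%; it falls below the 80% cut only at n of 18 or fewer (288/361 = 79.8%).

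**(c) Medications**
- Under section 5.7.1 a partial start is set to the first dose date if it shares the month and year (or, with the month missing, the year) of first dose. Otherwise it is set to the first of the month or year.
- The second route cannot put the start after the stop when the recorded dates are consistent. The first route can, but only if the drug stopped before first dose. With consistent dates, therefore, the section 5.7.3 fallback catches only drugs that are not concomitant under section 6.4.
- Illustration: first dose 15 Mar 2020, start recorded as 2020 only. Any stop from 1 Jan to 14 Mar (31 + 29 + 14 = 74 days) is classed as concomitant. If the AT1001-020 End of Study Visit is on the first-dose day, the last 14 of those days fall within the protocol's two-week allowance. That leaves 60 days of stops for which neither section 6.4 nor the protocol supports the result.
- With start recorded as Mar 2020, the affected stops are 1 to 14 March, all inside that allowance.

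**The case against.** All three rules act only on missing or partial dates, and nothing shows that any exist. Birth dates come from Study AT1001-020, an age of 0 would be noticed at output review, and protocol section 9.2.4.4.1 has each dose dated in a diary. The analysis is descriptive, with no testing. This all stands and limits the size of the point. It does not make the rules correct.

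On (b), the last dated diary dose is not a safe substitute. The diary sits in the drug wallet, so if the last wallet is not returned, the last dated dose belongs to the previous supply. With all 90 doses taken, the true last dose is 178 days after dispensing and the last dated one 2 days before it, so exposure would be understated by 180 days. This stands, and the fix allows for it.

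On (c), protocol section 11.4.4.8 agrees with the section 5.7.3 result for recent stops, and drugs stopped earlier may seldom reach this study's records. Dates can also conflict: with first dose 15 Mar 2020, start May 2020 and stop 10 Apr 2020, the fallback fires for a drug recorded as stopping after first dose. Classing every such drug as prior would therefore be wrong. Both points stand.

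Stronger readings that a reader might infer are not supported:
- *Age 0 distorts subgroup results.* The SAP's subgroups are sex and ERT status, so no subgroup table changes.
- *TEAE counts are affected.* SAP section 9.2 defines a TEAE from first dose alone, so counts and percentages of subjects do not move; only the exposure-based rate does.
- *Compliance is always understated.* That depends on what total dose received means, which SAP section 9.1 leaves undefined.
- *All drugs stopped before first dose are misclassed.* A partial start date in the month or year of first dose is needed.

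**Conclusion.** The point holds in a limited form. A partial birth date always gives age 0; this needs no assumption beyond the date being partial. A missing last-dose date for a subject who stops partway through a supply lengthens exposure by 2S + 2 − 2n days, and one 92-day case lowers the TEAE incidence rate by about 0.6% to 1.7%. Those figures rest on the assumed supply size and the assumed 45 to 15 patient-years. If the supply is used up, the error is only 2 days. The medication rule contradicts SAP section 6.4 for a narrow set of records, and the clear error is for stops outside the protocol's two-week allowance. The frequency of triggering is not stated, and the study-level effect is probably small. The rules should be corrected because they are wrong as written and cheap to repair; the study's conclusions are not shown to be at risk.

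**What to change.** - **(a)** In SAP section 5.7.5, change *prior to* to *after*, or delete the sentence.
- **(b)** In SAP section 5.7.4, cap the imputed last-dose date at the earliest of recorded treatment discontinuation, ET visit, death and last contact. The discontinuation date is itself an upper bound, since it can be later than the last dose. Use the last dated diary dose only where the diary for the last dispensed supply is available. State in section 9.1 how total dose received is obtained.
- **(c)** In SAP section 5.7.3, resolve a start-after-stop conflict by using the stop date, as section 5.7.1 does for adverse events, and then classify by section 6.4. Do not class all such drugs as prior. Reconcile sections 5.7.3 and 6.4 with the two-week rule in protocol section 11.4.4.8, and record any departure in SAP section 12, which at present declares none for medications.

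The cost is one word, a few sentences, one definition and minor programming. Only data already collected are used.
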